Instruct subjects and parents/caregivers to refer primary healthcare providers to the investigational center staff if they have any questions about study devices and their functions		х	х	х	х	х	х	х	х	x	х	х
Instruct subjects and their parents/caregivers that they should not assume that SmartGuard is able to prevent all hypoglycemia or all hyperglycemia including diabetic ketoacidosis		х				Х						
Instruct study subjects and parents/caregivers that regular weekly uploads of the study pump is required.		х	Х	X	Х	X	Х	Х	Х	Х	Х	

D00459338

Version E

Page 84 of 159

Medtronic

			Run-In	Period				S	tudy Period			
	Visit 1 (Office)	Visit 2 (Office or Virtual Office)	Visit 3* and 4* (Phone)	Visit 5 (Phone)	Visit 6 (Office or Virtual Office)	Visit 7 (Office or Virtual Office)	Visit 8* (Phone)	Visit 9, 10 & 11 (Phone)	Visit 12 (Office or Virtual Office)	Visit 13 (Phone)	Visit 14 (Office or Virtual Office)	Visit 15** (Office or Virtual Office)
Visit Window	Enrollment		Day 1 and Day 3 after Visit 2	Day 7 (±2 days) after Visit 2	Day 14 (±3 days) after Visit 2	Day 7 (-7 days) after Visit 6	Day 2 after Visit 7	Day 7 (±2 days) after Visit 7 Day 14 and Day 21 (±3 days) after Visit 7	Day 28 (+7 days) after Visit 7	Day 44 (±3 days) after Visit 7	Day 60 (+7 days) after Visit 7	Day 90 (+7 days) after Visit 7 EOS
With Bluetooth connection and the MiniMed Clinical app/MiniMed Mobile app, scheduled uploads are not required for subjects with compatible smartphones, as they are designed to occur continuously. Subjects that do not have compatible smartphones will be required to use the Blue Adapter to facilitate uploads to their computers.												
Instruct subjects and their parents/caregivers to give meal bolus of insulin 15-20 minutes prior to meals during the run-in period		х										
Instruct subjects and their parents/caregivers to give meal bolus of insulin at the start of meals during the study period						Х						

* Required for subjects without CGM or closed loop experience; as needed for all others. **When subjects exit the study early, all requirements that are listed for the final visit apply.

D00459338

Version E

9.2 Data Collection

All data collection and study procedure requirements are described at the subject visits in **Section 9.1**.

9.3 Subject Consent

Informed Consent and assent (if applicable) will be obtained in accordance with ISO14155:2020, the Code of Federal Regulations (CFR) Title 21, Part 50 (US only) or Tri-Council Policy Statement, Article 3.2 (Canada only). Prior to entry into the study, the California Experimental Subject's Bill of Rights (if applicable, US only), the EC (Ethics Committee)/Institutional Review Board (IRB) and Medtronic approved ICF form and assent form (if an assent form is required per local regulations) and an Authorization Form required by the Health Insurance Portability and Accountability Act (HIPAA; US only) will be presented to each subject to review and sign as applicable. The subject and their parent, guardian, or legally authorized representative (as applicable) will be given ample time and offered the opportunity to review these documents away from the investigational center.

If the subject is below 18 years of age, he/she should be informed about the study to the extent compatible with the subject's understanding. Per EC/IRB, if the subject could give consent to decisions about participation in research, the investigator must obtain that consent in addition to the consent of their legally authorized representative or guardian. Consent by a legal guardian or authorized representative is only allowed for subjects who are younger than legal age according to their state/country requirements.

The following will be provided to or explained to the subject and their parent, guardian, or legally authorized representative by the investigator or designee: the purpose and duration of the study, the requirements expected to be adhered to by the subject during the study and the potential risks /potential benefits associated with participation in the study. Every attempt will be made to answer the subject's and their parent's, guardian's, or legally authorized representative's questions during the informed consent and assent process. The language used shall be as non-technical as possible and must be understandable to the subject or their parent, guardian, or legally authorized representative.

Neither the investigator, nor the investigational center staff shall coerce or unduly influence a subject or their parent, guardian, or legally authorized representative to participate or to continue to participate in the clinical study. The informed consent/assent process shall not waive or appear to waive the subject's rights. The assent, if required, should be administered according to the investigational center's Standard Operating Procedures (SOPs) and the EC/IRB instructions, as applicable.

Subjects will complete California Experimental Subject's Bill of Rights (if applicable, US only), the HIPAA Form (US only), and the ICF/assent form. The consenting process must be documented in the subject's source documents. The subject and their parent, guardian, or legally authorized representative will receive copies of the fully executed documents. A subject's participation in study procedures cannot begin before the consent process has been properly executed. When the subject decides to participate in the

CIP336 Clinical Investigation Plan Medtronic D00459338 Version E Page 86 of 159

study, the ICF must be signed and personally dated by the subject and investigator or authorized designee, as required by the ICF. A patient contact card will be provided to the subject.

Medtronic will inform the investigators whenever information becomes available that may be relevant to the subject's confirmed participation in the clinical study. The investigator or his/her authorized designee should inform the subject and their parent, guardian, or legally authorized representative in a timely manner.

Medtronic will revise the written ICF/assent form whenever new information becomes available that may be relevant to the subject's confirmed participation in the clinical study. The revised information will be sent to the investigator for approval by the EC/IRB. After approval by the EC/IRB, a copy of this information must be provided to the participating subjects, and the informed consent/assent process as described above needs to be repeated.

If the ICF/assent form is amended during the course of the study, the EC/IRB will determine:

- Whether or not active subjects and their parent, guardian, or legally authorized representative should be re-consented at their next visit and
- Whether or not subjects who have completed the study at the time of the amendment should be re-consented .

Subjects and their parent, guardian, or legally authorized representative will be informed that qualified personnel from the investigational center, the sponsor (Medtronic), regulatory authorities such as the FDA/Health Canada and/or the EC/IRB, may have access to the clinic records that reveal their identity and health care information.

The investigational center must report the following informed consent/assent violations to their EC (if applicable)/IRB and sponsor:

- Failure to obtain informed consent/assent from subject and their parent, guardian, or legally authorized representative.
- Failure to obtain informed consent/assent prior to performing one or more study procedures.
- Failure to maintain ICFs/assent forms on file for all subjects who have provided informed consent.
- Use of an ICF/assent form that has not received approval from the EC/IRB.
- Use of an incorrect version of the ICF/assent form.

9.4 Safety Monitoring/Risk Analysis

9.4.1 Glucose Monitoring Risk

D00459338

- Subjects will be instructed to make sure they have clean fingers when performing fingerstick glucose testing.
- Subjects will have training on diabetes self-management principles.

Version E

9.4.2 Hypoglycemic/Hyperglycemic Risk

Intervention and treatment for hypoglycemia and hyperglycemia is addressed in **Section 10.1**.

9.4.3 Calibration of CGM Risk

When an erroneous glucose value is used to calibrate a CGM, this can result in inaccurate SG values. Subjects will be trained on appropriate calibration.

9.4.4 Reuse Risk

All study devices will be single patient use.

9.4.5 Sterilization Risk

The following devices will be supplied sterilized:

- Infusion sets
- Insulin reservoirs
- Sensors

9.4.6 Misuse Risk

Comprehensive training will take place at the initiation visit for investigational center staff regarding the operation of the 780G system, to include all of its functional components and all other study devices to be used during the study at the investigational center.

D00459338

9.4.7 Risk of Blood Sample Collection, Contamination from Sampling Techniques

Detailed mitigations to blood sampling risk are provided in **Section 10.1**.

9.4.8 HbA1c Risk

A Central laboratory will be used for HbA1c testing.

9.5 Glucose and Glycemia Measurements

During the course of the study, the subjects' BG levels, SG levels, HbA1c, and blood ketones will be collected using the methods outlined in this section.

9.5.1 **Daily Blood Glucose**

Values will be assessed during the study by all subjects using the Accu-Chek Guide Link study meter. The control solution test will be performed following the manufacturer's user guide. Subjects will be trained on the use of the Accu-Chek Guide Link study meter per the manufacturer's instructions.

9.5.2 Blood Ketone Values

Blood ketones will be measured by all subjects using a ketone meter when certain conditions are met:

- When a subject is symptomatic for high blood glucose
- When sensor glucose displays a glucose value >300mg/dL (16.7 mmol/L), BG should be checked by fingerstick and, if BG is >300mg/dL (16.7 mmol/L), blood ketones should be checked.

The control solution test will be performed following the manufacturer's user guide. The investigational center staff will be trained on the use of the ketone meter per the manufacturer's instructions. All ketone measurements will be reported by study subjects.

9.5.3 Sensor Glucose Values

SG data will be collected by subject's study pump and calibrated by each subject's Accu-Chek Guide Link study meter.

9.5.4 **HbA1c**

HbA1c is collected at baseline and the end of subjects' participation; if subjects have completed Visit 7 and exit early, a HbA1c will be collected.

D00459338

Version E

Page 89 of 159

9.6 Recording Data

Data entered by the investigational center staff will be captured on eCRFs using the Electronic Data Capture (EDC) system. Original eCRFs will not be considered as source data and supporting documentation will be required. In addition, the subject will complete the questionnaires online via direct entry. In case the online link is unavailable, subjects will complete the questionnaire using a paper format (this will be source data) and subsequently the investigator or designated investigational center staff will enter the responses online. If paper format is used, the investigator or designated investigational center staff should maintain the original paper source in the subject's source file.

Electronic device data will be collected from the study pump using CareLink Personal/CareLink system software. The system uses TLS technology, which encrypts all data it stores (21 CFR Part 11 compliant). Certain data points stored in the downloaded information may also be captured on the appropriate eCRF. Electronic device data could also be collected by the MiniMed Clinical app/MiniMed Mobile app and the CareLink Clinical app.

The investigator will ensure that all eCRFs are completed promptly, completely, and accurately. Medtronic will provide detailed instructions to assist with eCRF completion. In the event of data discrepancies, investigational centers will be asked to resolve queries electronically in the EDC system; otherwise, irresolvable data-related issues will be routed to the sponsor for review and final disposition. An audit trail is maintained in the EDC system to capture any corrections or changes of the eCRFs. System backups for data stored in the EDC system will be consistent with Medtronic SOPs.

Medtronic will only consider eCRFs to be complete when all discrepancies between source data and eCRF have been resolved. eCRF content will be reviewed by a study monitor, as described in the Monitoring Plan. In addition, specific eCRFs must also be reviewed and electronically signed by the investigator, indicating his/her agreement with the accuracy of all recorded data. It is expected that the investigator and his/her staff will cooperate with the monitoring team and provide any missing data in a timely manner.

9.7 Deviation Handling

A deviation is any instance(s) of failure to follow, intentionally or unintentionally, the requirements of the CIP. It is expected that the investigator will conduct this clinical trial in compliance with the CIP and all applicable regulations governing the conduct of clinical research involving human subjects. Failure to do so could result in one or all of the following:

- Investigational center disqualification
- Notification to the regulatory authorities/EC/IRB depending on the severity of the deviation and reporting requirements

The investigator should not implement any deviation from, or changes to, the CIP without agreement by the sponsor and prior review and documented approval/favorable opinion from the regulatory authority (if applicable) or EC (if applicable)/IRB, except where necessary to eliminate an immediate hazard(s) to trial subjects. The use of waivers from the CIP are prohibited in this study.

CIP336 Clinical 1	Investigation Plan		
D00459338	Version E	Page 90 of 159	Med

ronic

9.7.1 **Documenting Requirements for Study Deviations**

9.7.1.1 Unplanned CIP Deviations

The investigator may encounter the need to deviate from the CIP when necessary to protect the safety, rights or well-being of a subject in an emergency or in unforeseen situations beyond the investigator's control (e.g., subject failure to attend scheduled follow-up visits, inadvertent loss of data due to computer malfunction, inability to perform required procedures due to subject illness).

Deviations from the CIP, regardless of the reason should be documented as soon as possible, after the deviation occurs or is identified. This documentation should include deviation date, description of the deviation, the reason for deviation, and the corrective action. Refer to **Table 9 (US)** and **Table 10 (Canada)** for reporting timelines for emergency deviations.

CIP deviations should be reported as follows:

- a) To the EC(if applicable)/IRB for notification/acknowledgement;
- b) To the sponsor and, if required;
- c) To the applicable regulatory authority (reported by sponsor).

9.7.2 **Reporting Requirements for Study Deviations**

All study deviations must be reported on the eCRF regardless of whether medically justifiable, an inadvertent occurrence, or taken to protect the subject in an emergency. The date, description, and reason for each deviation will be documented.

The following examples are deviations that could impact subject safety, affect the integrity of study data and/or affect subject's willingness to participate in the study. These deviations are significant and require immediate sponsor notification upon investigator awareness:

- Failure to obtain informed consent/assent, i.e., there is no documentation of consenting
- Informed consent/assent obtained after initiation of study procedures
- Continuation of a subject who did not meet all inclusion/exclusion criteria
- Performing study procedure not approved by the EC/IRB
- Failure to inform EC/IRB and sponsor of reportable AEs (see Section 11)
- Investigational study device dispensed without obtaining informed consent/assent

In the event the deviation involves a failure to obtain a subject's consent, or is made to protect the life or physical well-being of a subject in an emergency, the deviation must be reported to Medtronic as well as the EC/IRB ,if applicable per local regulations, within five (5) working days.

CIP336 Clinical I	nvestigation Plan		
D00459338	Version E	Page 91 of 159	Medtronic

Reporting of all other study deviations should comply with:

- EC/IRB policies and/or
- local laws and/or
- regulatory authority requirements

They must be reported to Medtronic as soon as possible upon the center becoming aware of the deviation. Refer to Investigator Reports, **Table 9 (US)** and **Table 10 (Canada)** for specific deviation reporting requirements and timeframes for reporting to Medtronic, EC/IRB, and regulatory authority (if applicable).

9.7.3 Analyzing Deviations

Medtronic is responsible for reviewing deviations, assessing their significance, and identifying any additional corrective and/or preventive actions (e.g., amend the CIP, conduct additional training, terminate the investigation). Repetitive or serious investigator compliance issues may result in initiation of a corrective action plan with the investigator and investigational center, and in some cases, necessitate suspending enrollment until the problem is resolved or ultimately terminating the investigator's participation in the study.

9.8 Subject Exit, Withdrawal or Discontinuation

Subjects may choose to withdraw from the study at any time by notifying investigational center staff of their intent.

If a subject chooses to end his or her study participation or if the subject is removed from the study at the investigator's discretion or for failure to meet the study requirements, the reason for withdrawal must be documented. All study devices and supplies must be returned (as applicable) and documented both in source documents and on an eCRF. Following study exit, subjects will receive standard medical care from their own providers.

A subject will be withdrawn from the study if:

- In the opinion of the investigator, the subject's health or safety would be compromised by continuing in the study (e.g., infection at skin site, severe skin reaction to adhesive).
- In the opinion of the investigator, it is in the subject's best interest to discontinue participation in the study.
- During the course of the study, subject begins using hydroxyurea.

CIP336 Clinical Investigation Plan Additional Plan Additional Plan D00459338 Version E Page 92 of 159 Medtronic

- During the course of the study, subject begins participation in another investigational study (drug or device).
- At the discretion of the investigator: During the study it becomes known that subjects are using a non-linked BG meter for SMBG or a system that replaces SMBG.
- During the course of the study, subject begins abusing illicit drugs.
- During the course of the study, subject begins abusing marijuana.
- During the course of the study, subject begins abusing prescription drugs.
- During the course of the study, subject begins abusing alcohol.
- During the course of the study, subject begins using pramlintide (Symlin), DPP-4 inhibitors, liraglutide (Victoza or other GLP-1 agonists), metformin, canagliflozin (Invokana or other SGLT2 inhibitors).
- During the course of the study, subject receives red blood cell transfusion or erythropoietin.
- During the course of the study, the subject demonstrates that he/she is not able to comprehend instructions for study procedures, as evaluated by the appropriate research staff.
- During the study, a subject repeatedly activates SmartGuard feature when instructed otherwise, e.g., SmartGuard feature is turned on (as applicable at the discretion of the investigator).
- During the course of the study, subject is taking oral, injectable, or IV glucocorticoids
- During the study, (female) subject becomes pregnant.
- During the study, the subject experiences one severe hypoglycemic episode, if it is related to the use of 780G system SmartGuard feature.
- During the study, the subject experiences one episode of DKA, if it is related to the use of 780G system SmartGuard feature.
- During the study, subject has a cardiovascular event or any vascular event such as stroke.

Documentation of the reason(s) leading to subject withdrawal will be kept in the subject's source documentation.

9.8.1 End of Subject Participation in Study/ Completion of Study

After the study has been completed (at Visit 15 or in case of early termination), subjects will be exited from the study. Subjects will continue to work with their physician after study exit per normal standard of care. The clinical investigation is considered completed once the last subject has exited the study.

9.8.2 Lost to Follow-Up

If a subject does not return to the site for required follow-up visit(s) and cannot be reached, the investigation site personnel should make 3 documented attempts to contact the subject by phone to verify if the subject should be considered "lost-to follow up". In the event the subject is not able to perform follow-up visits at the investigation site, subject will be considered "lost to follow up" and this

CIP336 Clinical Investigation Plan Image: Compage 93 of 159 Medtronic D00459338 Version E Page 93 of 159 Medtronic

needs to be documented in the Study Exit eCRF. All efforts will be made by investigation site personnel to collect all study devices and supplies back from subject, if applicable.

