9.1 Schedule of Events

Subjects may participate in up to 15 planned study visits, as presented in **Figure 4 (Section 9.1.1)** for approximately 120 days of device wear. Virtual office visit (audio visual) may be performed for office visits in cases where an office visit is not possible. The exit visit should occur at the office, unless an emergent situation occurs.

If the subject visits the investigational center outside of the scheduled study visits, a Visit eCRF will be completed to document the reason for the unscheduled visit.

Refer to **Section 9.1.1**, **Table 5** for the Visit Details.

If subject exits the study early (i.e., before their last scheduled visit), HbA1c requirements that apply to the final visit will be completed for subjects who have completed Visit 7. Refer to CIP336 Questionnaire Guide for collection of early exit requirements.

The Exit eCRF and all associated activities should be completed for all subjects who have withdrawn, discontinued, or completed the study.

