 - Ask subjects about adverse events and device performance
 - Review CareLink reports
 - Remind subjects about meal/exercise challenges for 120 mg/dL (6.7 mmol/L) setpoint
- Visit 9 (Phone): Day 7 (±2 days) after Visit 7
 - Adjust pump settings as needed
 - Ask subjects about adverse events and device performance
 - Review CareLink reports
 - Remind subjects about meal/exercise challenges for 120 mg/dL (6.7 mmol/L) setpoint
- Visit 10 (Phone): Day 14 (±3 days) after Visit 7
 - Adjust pump settings as needed
 - Ask subjects about adverse events and device performance
 - Review CareLink reports
 - Instruct subjects about the required meal/exercise challenges for 120 mg/dL (6.7 mmol/L) setpoint
- Visit 11 (Phone): Day 21 (±3 days) after Visit 7
 - Adjust pump settings as needed
 - \circ $\;$ Ask subjects about adverse events and device performance
 - Review CareLink reports
 - Change Auto Basal target to 100 mg/dL (5.5 mmol/L) setpoint with Active Insulin Time set to 2-3 hours or at investigator's discretion
 - Remind subjects about meal/exercise challenges for 100 mg/dL (5.5 mmol/L) setpoint
- Visit 12 (Office/Virtual Office): Day 28 (+7 days) after Visit 7
 - Ask subjects about adverse events and device performance
 - Review CareLink reports
- Visit 13 (Phone): Day 44 (±3 days) after Visit 7
 - Adjust Auto Basal target with Active Insulin Time at investigator's discretion
 - Ask subjects about adverse events and device performance
 - Review CareLink reports
 - Remind subjects about meal/exercise challenges

D00459338

•

- Review CareLink reports
- Visit 15 (Office/Virtual Office): Day 90 (+7 days) after Visit 7

Visit 14 (Office/Virtual Office): Day 60 (+7 days) after Visit 7

- Ask subjects about adverse events and device performance
- Review CareLink reports
- Return study devices
- End of Study (EOS)

Figure 4. Visit Schedule

Medtronic Business Restricted

CONFIDENTIAL 056-F275 Rev E Clinical Investigation Plan Template

CIP336 Clinical I	nvestigation Plan		
D00459338	Version E	Page 70 of 159	Mectronic

Table 5. Visit Details

		Run-In Period					S	tudy Period				
	Visit 1 (Office)	Visit 2 (Office or Virtual Office)	Visit 3* and 4* (Phone)	Visit 5 (Phone)	Visit 6 (Office or Virtual Office)	Visit 7 (Office or Virtual Office)	Visit 8* (Phone)	Visit 9, 10 & 11 (Phone)	Visit 12 (Office or Virtual Office)	Visit 13 (Phone)	Visit 14 (Office or Virtual Office)	Visit 15** (Office or Virtual Office)

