Collect study devices at study end (see device disposition Table 3 [US] and Table 4 [Canada] for details)												х

D00459338

Version E

Page 79 of 159

Medtronic

			Run-In	Period				S	tudy Period			
	Visit 1 (Office)	Visit 2 (Office or Virtual Office)	Visit 3* and 4* (Phone)	Visit 5 (Phone)	Visit 6 (Office or Virtual Office)	Visit 7 (Office or Virtual Office)	Visit 8* (Phone)	Visit 9, 10 & 11 (Phone)	Visit 12 (Office or Virtual Office)	Visit 13 (Phone)	Visit 14 (Office or Virtual Office)	Visit 15** (Office or Virtual Office)
Visit Window	Enrollment		Day 1 and Day 3 after Visit 2	Day 7 (±2 days) after Visit 2	Day 14 (±3 days) after Visit 2	Day 7 (-7 days) after Visit 6	Day 2 after Visit 7	Day 7 (±2 days) after Visit 7 Day 14 and Day 21 (±3 days) after Visit 7	Day 28 (+7 days) after Visit 7	Day 44 (±3 days) after Visit 7	Day 60 (+7 days) after Visit 7	Day 90 (+7 days) after Visit 7 EOS
Note: If the visit must be conducted via Virtual Office, the blood tests may be												
collected via mobile phlebotomy service.												
Questions To Ask at Study Visits	L .	-	-		-	L .	-	-	_		_	
Ask if subjects and their parents/caregivers have general study- related questions and concerns	Х	х	х	х	х	х	х	х	х	х	х	х
Ask subjects about the occurrence of adverse events.												
 Record the event on the appropriate eCRF, if a study subject reports a change in health status that results in a new medical condition or in a deterioration of an existing medical condition, such as illness or glycemic problems Instruct subject to call the investigational center to report any changes to their health status (see adverse event definition). 		Х	x	X	X	x	x	x	X	X	X	x

D00459338

Version E

Page 80 of 159

Medtronic

			Run-In	Period				Si	tudy Period			
	Visit 1 (Office)	Visit 2 (Office or Virtual Office)	Visit 3* and 4* (Phone)	Visit 5 (Phone)	Visit 6 (Office or Virtual Office)	Visit 7 (Office or Virtual Office)	Visit 8* (Phone)	Visit 9, 10 & 11 (Phone)	Visit 12 (Office or Virtual Office)	Visit 13 (Phone)	Visit 14 (Office or Virtual Office)	Visit 15** (Office or Virtual Office)
Visit Window	Enrollment		Day 1 and Day 3 after Visit 2	Day 7 (±2 days) after Visit 2	Day 14 (±3 days) after Visit 2	Day 7 (-7 days) after Visit 6	Day 2 after Visit 7	Day 7 (±2 days) after Visit 7 Day 14 and Day 21 (±3 days) after Visit 7	Day 28 (+7 days) after Visit 7	Day 44 (±3 days) after Visit 7	Day 60 (+7 days) after Visit 7	Day 90 (+7 days) after Visit 7 EOS

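### Protocol 9.8.2 labels a subject who cannot attend on site as lost to follow-up even if reachable, in conflict with the virtual-visit provisions of 9.1 and Table 5

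*Protocol*

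**What the plan says.** Protocol 9.8.2 contains two rules. The first covers a subject who fails to return and "cannot be reached, the investigation site personnel should make 3 documented attempts to contact the subject by phone". The second reads "In the event the subject is not able to perform follow-up visits at the investigation site, subject will be considered" lost to follow-up. It requires an entry on the Study Exit eCRF, and the section ends by asking the site to recover the study devices. The second rule mentions neither reachability nor virtual visits.

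Protocol 9.1 treats the same situation differently: "Virtual office visit (audio visual) may be performed for office visits in cases where an office visit is not possible". The next sentence narrows this for the last visit: "The exit visit should occur at the office, unless an emergent situation occurs". The visit list in 9.1.1 nevertheless gives "Visit 15 (Office/Virtual Office): Day 90 (+7 days) after Visit 7". In 9.1.1 and Table 5, Visits 2, 6, 7, 12, 14 and 15 are all office or virtual office. The other visits after Visit 1 are by telephone.

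A note in Table 5 provides for remote sampling: "If the visit must be conducted via Virtual Office, the blood tests may be" "collected via mobile phlebotomy service".

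For early exit, 9.1 states that "HbA1c requirements that apply to the final visit will be completed for subjects who have completed Visit 7". Section 9.5.4 and the Table 5 footnote say much the same.

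**The concern.** Take a subject who is ill at home or has moved away, but who answers calls and uploads the pump. Section 9.1 keeps that subject in the study and the second rule of 9.8.2 exits the same subject. Nothing says which passage prevails, so sites may act differently.

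Both primary endpoints depend on late data. The safety endpoint is the HbA1c change to the end of the 3-month study period (Protocol 14.5.1, SAP 7.9.2). All effectiveness endpoints use data from Visit 13 to the end of the study (SAP 7.9.3). Being unable to travel can reflect poor health, so the resulting missingness could be informative. The disposition summary (Protocol 14.2, SAP 7.1.2) would also count contactable people as lost.

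**Working it through.** The documents give no figure to reproduce here. The visible text states no drop-out rate, standard deviation or power. The check is mainly a comparison of passages.

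**1. Same trigger, opposite result.**
- 9.8.2, first rule: does not return and cannot be reached, three telephone attempts, then possibly lost to follow-up.
- 9.8.2, second rule: cannot do visits on site, then lost to follow-up, with no further condition.
- 9.1 and Table 5: office visit not possible, then a virtual visit.

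The second rule removes the condition that gives the first its meaning. Its trigger is in substance the one that 9.1 uses to allow a virtual visit.

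**2. Where the mobile-phlebotomy note applies.** Table 5 schedules HbA1c only at Visits 1 and 15, and the other laboratory samples only at Visit 1. Visit 1 is office only. The one scheduled blood draw that can fall at a virtual visit is therefore the Visit 15 HbA1c. The protocol thus has a remote route to the primary safety endpoint, and the second rule of 9.8.2 closes it.

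**3. What an exited subject loses.** Inputs: Visit 13 at Day 44 (±3), Visit 15 at Day 90 (+7), both counted from Visit 7.
- Effectiveness window: 90 − 44 = 46 days nominal; shortest 90 − 47 = 43; longest 97 − 41 = 56.
- Exit at Visit 12 (Day 28): no sensor data in the window. The early-exit HbA1c is drawn 90 − 28 = 62 days before the nominal endpoint.
- Exit at Visit 14 (Day 60): 60 − 44 = 16 window days kept, 46 − 16 = 30 lost. The HbA1c is 90 − 60 = 30 days early.
- In either case the subject leaves the per-protocol set, which requires completing the study period (SAP 7.1.4).

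**4. Effect on precision (illustration; loss rates and SDs are assumed).** With a fraction d lost, the standard error grows by 1/√(1 − d).
- d = 2%: 1.010
- d = 5%: 1.026
- d = 10%: 1.054
- d = 15%: 1.085

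One-sample non-inferiority power is approximately Φ(margin·√n/SD − 1.96), with the true mean equal to the threshold. For HbA1c (margin 0.4), n = 100 against n = 90:
- SD 0.75: 0.9996 against 0.999
- SD 1.0: 0.979 against 0.967
- SD 1.2: 0.915 against 0.885

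For time in range (margin 7.5, SD 8 to 12), power stays above 0.999 even at n = 85.

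**The case against.** The strongest reply is that the protocol already protects most of the data. Three places require a final-visit HbA1c from anyone who exits early after Visit 7, and a reachable subject can provide one. Sensor data uploaded before exit are kept, and uploads run continuously or from home. The ITT set includes everyone who starts the study. The second rule sits directly after the three-attempts procedure and could be read as its conclusion, and the withdrawal list in 9.8 has no criterion for inability to travel.

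Much of this stands, and it rules out three stronger readings that a reader might infer.
- **That each affected subject loses the HbA1c pair.** After Visit 7 an early-exit value is required. What may be lost is its timing at the end of 3 months. The visible text does not say whether the early-exit duty extends to subjects labelled lost to follow-up.
- **That no visit after screening needs site attendance.** Virtual visits are conditional, and 9.1 expects the exit visit at the office unless the situation is emergent. That sentence is not fully aligned with the office-or-virtual label on Visit 15.
- **That the trial's power is at risk.** The illustration shows little effect at plausible loss rates.

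The contradiction itself is not answered. Membership of the ITT set does not supply values that were never recorded. The kinder reading of the second rule has to add a condition that its words do not contain. SAP 7.4, where the revision history places an imputation method, is not in the public text, so nothing is claimed about how missing values would be handled.

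**Conclusion.** The point holds as a contradiction that creates a risk of data loss, not as a stated loss. If a site follows the second rule of 9.8.2, a reachable subject is exited. That subject may lose the 3-month HbA1c and any sensor data after exit, up to the full nominal 46-day window if exit precedes Visit 13, and is reported under the wrong disposition.

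The number affected is not given. At an assumed 2% to 5% of 100 subjects per cohort, 2 to 5 subjects would be affected and the standard error would rise by about 1.0% to 2.6%. The weight of the point lies in missing data that are avoidable and possibly related to health. That relation is plausible but not shown in the documents. The correction should be made because it is cheap and uses provisions the protocol already has.

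**What to change.** - In Protocol 9.8.2, limit loss to follow-up to subjects who cannot be reached after the three documented attempts, and remove the rule based only on site attendance.
- Add that a reachable subject who cannot attend on site continues by virtual visit and remote upload, with the Visit 15 HbA1c collected by mobile phlebotomy.
- Reconcile this with the exit-visit sentence in 9.1 and the Visit 15 label in 9.1.1 and Table 5. Changing 9.8.2 alone would leave a new conflict with the emergent-situation condition.
- Record any actual exit under its true reason.

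The cost is a few sentences across 9.8.2 and 9.1, and a few more mobile blood draws. Virtual visits, home upload and mobile phlebotomy are already provided for.
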